## 9.4.5 Adjustments for Covariates

In general, the two randomization stratification factors (type of phosphate binder and s-P level at Visit 1) will be adjusted in inferential analyses of efficacy endpoints on FAS (Cohorts 1-2). Baseline value may also be adjusted if applicable. Detailed information on covariate adjustment will be provided in the SAP.

#### 9.4.6 Visit Windows

No analysis visit windows will be formally defined. The schedule of assessments and procedures in Section 1.3 details the intended collection of study variables at specified visits. Data collected at a scheduled visit will be used as the data at the corresponding analysis visit even if the visit is out-of-window. To minimize the amount of missing data, data collected at an unscheduled visit will be mapped to an analysis visit based on analysis windows if data at the corresponding scheduled visit are not available. Similarly, data from the Early Termination visit may also be mapped. Detailed information on analysis windows will be provided in the SAP.

#### 9.4.7 Safety and Tolerability Analyses

Safety analyses include summaries for AEs, physical examination, body weight, vital signs, 12-lead ECG, and safety laboratory tests.

All AEs will be coded using the Medical Dictionary for Regulatory Activities (MedDRA). Treatment-emergent AEs will be tabulated by MedDRA system organ class and preferred term. Listings will also be provided for AEs and AEs of special interest.

Other safety measures will be summarized descriptively by cohort and visit.

As a tolerability analysis, stool frequency and consistency collected on a daily basis throughout the 10-week Treatment Period will be summarized (for Part A only) on a weekly basis (i.e., average weekly stool frequency and average weekly stool consistency).

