#### **Safety Analyses:**

All safety and tolerability measures will be summarized descriptively by cohort and for the entire Safety Population. Treatment-emergent AEs will be summarized by MedDRA system organ class and preferred term. Stool frequency and consistency collected on a daily basis throughout the study will be summarized on a weekly basis (i.e., average weekly stool frequency and average weekly stool consistency).

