- Normal s-P and pill number response: achieving normal s-P response and pill number response
- Normal s-P and pill burden response: achieving normal s-P response, pill weight response, and pill number response
- Borderline s-P and medication dose response: achieving borderline s-P response and medication dose response
- Borderline s-P and pill weight response: achieving borderline s-P

Protocol Number: TEN-02-402

Edition No. 2

response and pill weight response

- Borderline s-P and pill number response: achieving borderline s-P response and pill number response
- Borderline s-P and pill burden response: achieving borderline s-P response, pill weight response, and pill number response

The final list of efficacy endpoints will be provided in the statistical analysis plan.

Exploratory inferential analyses may be performed to compare efficacy endpoints between cohorts. Subgroup analyses by age, sex, race, phosphate binder type, baseline s-P, and ending therapy category (e.g., tenapanor alone, tenapanor  $+ \le 3$  tablets/day phosphate binder, or tenapanor  $+ \ge 3$  tablets/day phosphate binder) will be performed for selective endpoints.

Protocol Number: TEN-02-402

Edition No. 2

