## 3.2 Secondary Objectives

The secondary objectives of this study, for the treatment of hyperphosphatemia in CKD patients on dialysis who are phosphate binder naïve or on phosphate binder therapy, include:

- To evaluate the effect of tenapanor alone or in combination with phosphate binders to achieve various s-P levels (e.g., ≤4.5 mg/dL).
- To evaluate different strategies of initiating tenapanor for the control of s-P level.
- To evaluate the effect of different strategies of initiating tenapanor on stool frequency and consistency using a daily eDiary.
- To evaluate the effect of tenapanor on reducing daily phosphorus-lowering therapy pill burden (number of pills and total pill weight) when patients are started on or transitioned to tenapanor from current phosphate binder therapy.
- To evaluate the impact of patient education and use of standard of care medication on the tolerability management of tenapanor.
- To evaluate the tolerability of tenapanor when patients are started on or transitioned to tenapanor from current phosphate binder therapy.
- To evaluate patient experience with phosphorus management routine during study compared to before study.
- To evaluate the effect of tenapanor alone or in combination with phosphate binders on iFGF23 and PTH.
- To evaluate the effect of tenapanor alone or in combination with phosphate binders on the use of PTH-modifying medications.

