## 6.1.5 Method of Assigning Patients to Treatment Groups

After giving informed consent, patients will be allocated sequential enrollment numbers at Screening (Visit 1).

Specifically for patients on phosphate binder therapy, a stratified randomization scheme will be employed, with type of phosphate binder (sevelamer, calcium-based binder, iron-based

23 February 2021 CONFIDENTIAL Page 32 of 60

Protocol Number: TEN-02-402

Edition No. 2

binder, other non-sevelamer binder, or a combination of binders of different types) and s-P level at Visit 1 (<7.5 mg/dL or  $\ge 7.5 \text{ mg/dL}$ ) as two stratification factors. The CRO or designated independent statistician will prepare the randomization scheme in accordance with the CRO's standard operating procedures (SOPs) and the randomization plan, which reflect GCP standards. After meeting all of the inclusion/exclusion criteria, eligible patients on phosphate binder therapy will be randomized in a 1:1 ratio at Visit 2 (Day 1) to Cohort 1 or Cohort 2.

The randomization of this study will be implemented via an Interactive Response Technology (IRT). The IRT will allocate the cohort and provide the randomization number. The IRT will provide the appropriate number of bottles of tenapanor.

If a patient withdraws from the study, his/her enrollment and randomization numbers cannot be reused.

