#### 9.2 Determination of Sample Size

Approximately 300 CKD patients on dialysis and stable phosphate binder therapy will be randomized in a 1:1 ratio to Cohort 1 or Cohort 2 (~150 patients/cohort); and approximately 30 phosphate binder naïve patients with CKD on dialysis will be enrolled into Cohort 3. Overall, approximately 330 patients with CKD on dialysis will be randomized or enrolled in this study. The sample size of this study is not planned based on statistical considerations.

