#### 9.4 Statistical Methods

#### 9.4.1 General Considerations

All measures will be summarized descriptively by cohort. Descriptive statistics including the number of observations (n), mean, standard deviation, median, minimum, and maximum will be presented for continuous variables. Summary statistics for iFGF23 will also include geometric mean and geometric coefficient of variation %. Frequency (n) and percent (%) will be presented for categorical variables.

Individual patient data including relevant derived variables will be listed.

Analyses of efficacy endpoints will be performed on the FAS and subsets of FAS. Analyses of safety and tolerability measures will be performed on the Safety population. The statistical testing, if any, will be conducted at a significance level of 0.05 (two-sided).

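### The secondary objective on how initiation strategy affects stool frequency and consistency has no stated Cohort 1 versus Cohort 2 estimate or interval in Section 9.4.7

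*Combined protocol and SAP*

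**What the plan says.** **Objective.** Section 3.2, repeated in the synopsis (Section 1.2), includes: "To evaluate the effect of different strategies of initiating tenapanor on stool frequency and consistency using a daily eDiary". General tolerability has its own, separate objective in the same list.

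**Design.** Section 9.2: "Approximately 300 CKD patients on dialysis and stable phosphate binder therapy will be randomized in a 1:1 ratio to Cohort 1 or Cohort 2". Section 6.1.5 stratifies this randomisation by binder type (five categories) and Visit 1 serum phosphorus (two categories). Cohort 3, about 30 binder-naïve patients, is not randomised. Under Section 7.3.1 the diary is completed every day from Screening to the end of Part A.

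**Stool analysis.** Section 7.3 classes stool frequency and consistency as tolerability measures. Section 9.4.7 says they "will be summarized (for Part A only) on a weekly basis", as weekly averages. The synopsis adds: "All safety and tolerability measures will be summarized descriptively by cohort and for the entire Safety Population". Section 9.4.1 lists the statistics for continuous variables: n, mean, SD, median, minimum and maximum.

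**Between-cohort provisions.** The synopsis says: "Exploratory inferential analyses may be performed to compare efficacy endpoints between cohorts". Section 9.4.3, headed as efficacy analysis, allows optional comparisons of continuous and binary endpoints. Section 9.4.5 ties adjustment for the two stratification factors to efficacy endpoints on FAS (Cohorts 1-2).

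**Status of the SAP.** Section 9.1 says that a separate SAP will be provided and prevails where it differs from the protocol. No SAP text was in the material reviewed.

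**The concern.** An effect of different strategies can be seen only by setting one strategy against another. The trial has a randomised pair of strategies and daily diary data on both, which is what this objective needs. The protocol's analysis text then stops at parallel columns of summary statistics, and the tools for a contrast (a between-cohort comparison and adjustment for the randomisation factors) are described only for a class of endpoints to which the stool measures do not belong.

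What is at stake is how the objective is answered. From side-by-side weekly means, a chance gap between the cohorts may be read as a strategy effect, or a real one passed over, because the uncertainty of the gap is not shown. The study is open-label and Section 9.4.8 provides for ongoing informal summaries, so a contrast chosen after the data have been seen would also carry less weight than one written down now.

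**Working it through.** The plan states no power, effect size, SD or derived sample size, so there is no figure of its own to reproduce beyond the total: 150 + 150 + 30 = 330. Two questions can be checked: whether the protocol text covers the contrast, and whether the planned size would make the contrast informative.

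**1. Coverage**

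| Element needed for the objective | Efficacy endpoints | Stool outcomes |
|---|---|---|
| Summary by cohort | Yes (1.2, 9.4.3) | Yes (1.2, 9.4.7) |
| 95% interval within cohort | Yes, for response rates (9.4.3) | Not stated |
| Between-cohort comparison | Optional, exploratory (1.2, 9.4.3) | Not stated |
| Adjustment for stratification factors | Yes, for inferential analyses (9.4.5) | Not stated |

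**2. What can be recovered from the planned tables.** For one week, n, mean and SD per cohort give the crude difference and its interval: difference ± 1.96 × sqrt(SD1²/n1 + SD2²/n2). Two things cannot be recovered from those tables. One is an estimate adjusted for the stratification factors. The other is an interval for an average over several weeks, because its variance depends on the correlation between weeks within a patient, which weekly SDs do not show.

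**3. Precision of a Cohort 1 minus Cohort 2 difference**

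Inputs: 150 per cohort (Section 9.2). The 120 per cohort is an assumption, a 20% loss of diary data. The SD is not in the documents, so results are given in SD units.

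- 95% half-width = 1.96 × SD × sqrt(2/n)
- n = 150: 1.96 × sqrt(2/150) = 0.226 SD
- n = 120: 1.96 × sqrt(2/120) = 0.253 SD

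For illustration, take an assumed SD of 0.8, 1.0 or 1.5 stools/day for a weekly average. The half-width is then 0.18, 0.23 or 0.34 stools/day at 150 per cohort, and 0.20, 0.25 or 0.38 at 120. The SD-unit results apply equally to average consistency.

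**4. Number of intervals if every week is reported.** Ten weeks × two outcomes = 20 intervals. If there were no strategy effect and the intervals were independent, the chance that at least one excludes zero would be 1 − 0.95^20 = 64%. Correlation between weeks lowers this, but it is a reason to name one main summary per outcome.

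**5. Adjustment.** Five binder types × two phosphorus levels = 10 strata, so 300/10 = 30 patients per stratum on average, before any imbalance between binder types. Some strata may be sparse.

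**The case against.** The strongest reply is that this study is descriptive by intent. Section 9.2 says: "The sample size of this study is not planned based on statistical considerations". Even for the primary serum phosphorus response, comparisons between cohorts are optional and exploratory. Asking for an adjusted contrast on a secondary tolerability measure would treat it more firmly than the main efficacy outcome. That argument defeats any call for a hypothesis test or for power, and none is made here. It does not defeat an estimate with a nominal interval, which is itself descriptive and answers an objective that the protocol chose to list.

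The second reply is that the SAP may already contain the contrast. This stands as a limit on the point, which concerns the protocol text only. Sections 9.4.3 to 9.4.6 each send some detail to the SAP, but Section 9.4.7 does not.

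Three stronger readings are tempting, and the documents do not support them:

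- A reader might infer that the protocol confines cohort comparisons to efficacy. No sentence forbids a tolerability comparison, and the general rule on testing in Section 9.4.1 is not restricted to efficacy. The protocol is silent; it does not prohibit.
- A reader might infer that the report would hold no information on the strategy effect or its uncertainty. The crude weekly difference and interval can be derived, as shown in the working.
- A reader might infer that randomisation guarantees an unbiased contrast. The diary is self-reported in an open-label study, and Section 9.4.4 summarises observed data without imputation, so unequal dropout or diary completion could distort the comparison.

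**Conclusion.** The point holds for the protocol as supplied. The objective calls for a contrast between strategies, the design provides a randomised one, and the text names only by-cohort and pooled weekly summaries for it. What is missing is a stated, stratification-adjusted Cohort 1 minus Cohort 2 estimate with its interval. Neither a confirmatory test nor all trace of the comparison is at issue.

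The planned size is no obstacle: the half-width would be about 0.23 SD with 150 per cohort, or 0.25 SD with 120. These figures assume equal SDs, ignore any gain from adjustment, and depend on how much diary data is lost, for which the documents give no rate. The contrast covers Cohorts 1 and 2 only.

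This is a change worth making, not a flaw that invalidates the study. If the SAP already specifies the contrast, a cross-reference from Section 9.4.7 closes the point.

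**What to change.** In Section 9.4.7 and in the SAP, for Safety Population patients in Cohorts 1 and 2:

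1. Add the Cohort 1 minus Cohort 2 difference with a 95% interval for average stool frequency and for average stool consistency, adjusted for the two randomisation stratification factors. State in advance how sparse binder-type strata will be pooled.
2. Name one main Part A summary per outcome, for example the average over the 10 weeks from a repeated-measures model. Present the weekly differences as supportive.
3. Label the analysis descriptive, with nominal intervals and no multiplicity adjustment.
4. Report diary completion by cohort and week, and give the rule for a week with missing diary days.

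Cohort 3 stays in the by-cohort summaries and outside the contrast.

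The cost is a small amount of modelling and a few more table entries. It needs no new data, no more patients and no change to study conduct. The remaining drawback is that the intervals are not adjusted for multiplicity, so isolated weekly differences should not be over-read.

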#### 9.4.8 Interim Analysis

This is an open-label study. No formal interim analysis is planned for this study. Informal summaries of key measures based on preliminary data will be performed on an ongoing basis.

23 February 2021 CONFIDENTIAL Page 53 of 60

Protocol Number: TEN-02-402

Edition No. 2

#### 10 ACCESS TO SOURCE DATA/DOCUMENTS

The Investigator will provide direct access to source data and documents for individuals conducting study-related monitoring, audits, IRB/IEC review, and regulatory review. The Investigator will contact the Sponsor immediately if contacted by a regulatory agency about a site inspection.

The Investigator must inform the study patient that his/her study-related records may be reviewed by the above individuals without violating the patient's privacy of personal health information in compliance with Health Insurance Portability and Accountability Act of 1996.

Attention is drawn to the regulations promulgated by the FDA under the Freedom of Information Act providing, in part, that information furnished to Investigators and IRBs will be kept confidential by the FDA only if maintained in confidence by the Investigator and IRB. By signing this protocol, the Investigator affirms to the Sponsor that the Investigator will maintain, in confidence, information furnished to him or her by the Sponsor and will divulge such information to the IRB under an appropriate understanding of confidentiality with such board.

## 11 QUALITY CONTROL AND QUALITY ASSURANCE

The Sponsor or its designee will implement and maintain quality control and quality assurance procedures with written SOPs to ensure the study is conducted and data are generated, documented, and reported in compliance with the protocol, GCP, and applicable regulatory requirements.

### 11.1 Conduct of Study

This study will be conducted in accordance with the provisions of the Declaration of Helsinki and all revisions thereof (Tokyo 2004), and in accordance with the FDA Code of Federal Regulations (CFR §312.50 and §312.56) and the International Conference on Harmonisation (ICH) E6 Guidelines on good clinical practice (Integrated Addendum to ICH E6(R1): Guideline for Good Clinical Practice ICH E6(R2)). Specifically, this study is based on adequately performed laboratory and animal experimentation; the study will be conducted under a protocol reviewed by an IRB or IEC; the study will be conducted by scientifically and medically qualified persons; the benefits of the study are in proportion to the risks; the rights and welfare of the patients will be respected; the physicians conducting the study do not find the hazards to outweigh the potential benefits; and each patient will give his or her written informed consent before any protocol-driven tests or evaluations are performed.

23 February 2021 CONFIDENTIAL Page 54 of 60

Protocol Number: TEN-02-402

Edition No. 2

The Investigator may not deviate from the protocol without a formal protocol amendment having been established and approved by an appropriate IRB, except when necessary to eliminate immediate hazards to the patient or when the change(s) involve only logistical or administrative aspects of the study and are approved by the Medical Monitor. Any deviation may result in the patient having to be withdrawn from the study and may render that patient non-evaluable.

#### 11.2 Protocol Amendments

Only the Sponsor may modify the protocol. All amendments that have an impact on patient risk or the study objectives, or require revision of the ICF, must receive approval from the IRB prior to their implementation.

#### 11.3 Monitoring of Study

The Investigator will permit the site monitor to review study data as frequently as is deemed necessary to ensure data are being recorded in an adequate manner and protocol adherence is satisfactory. Monitoring visits can occur remotely, if necessary.

The Investigator will provide access to the source documents or provide certified copies of medical records for the Monitor to verify eCRF entries. The Investigator is expected to cooperate with the Sponsor or its designee in ensuring the study adheres to GCP requirements.

The Investigator may not recruit patients into the study until the Sponsor or its designee has conducted a detailed review of the protocol and eCRFs with the site staff and the site has been activated upon the Sponsor's approval. With agreement of the Sponsor, attendance at an investigator meeting may fulfill the Site Initiation requirement.

#### 12 ETHICS

## 12.1 Institutional Review Board/Independent Ethics Committee Approval

#### 12.1.1 Ethics Review Prior to Study

The Investigator will ensure that the protocol and consent form are reviewed and approved by the appropriate IRB prior to the start of any study procedures. The IRB will be appropriately constituted and will perform its functions in accordance with FDA regulations, ICH GCP guidelines, and local requirements as applicable.

23 February 2021 CONFIDENTIAL Page 55 of 60

Protocol Number: TEN-02-402

Edition No. 2

#### 12.1.2 Ethics Review of other Documents

In addition, the IRB will approve all protocol amendments (except for sponsor-approved logistical or administrative changes), written informed consent documents and document updates, patient recruitment procedures, written information to be provided to the patients, available safety information, information about payment and compensation available to patients, the Investigator's curriculum vitae and/or other evidence of qualifications, and any other documents requested by the IRB and regulatory authority as applicable.

#### 12.2 Written Informed Consent

The nature and purpose of the study will be fully explained to each patient (or the patient's legally responsible surrogate). Patients must be given ample time and opportunity to inquire about details of the trial, to have questions answered to their satisfaction, and to decide whether to participate. Written informed consent must be obtained from each patient (or guardian), prior to any study procedures being performed).

#### 13 DATA HANDLING AND RECORD KEEPING

#### 13.1 Data Reporting and Electronic Data Capture

#### 13.1.1 Electronic Case Report Forms (eCRFs)

The Investigator will be provided with eCRFs and will ensure all data from patient visits are promptly entered into the eCRFs in accordance with the specific instructions given. The Investigator must sign the eCRFs to verify the integrity of the data recorded.

#### 13.1.2 Laboratory Data

A list of the normal ranges for all laboratory tests to be undertaken forms part of the documentation to be collated prior to trial start. Medpace Reference Laboratories (MRL) has been selected to conduct all tests and all samples will be analyzed at MRL. The Investigator must maintain source documents such as laboratory reports and complete history and physical examination reports.

#### 13.1.3 Retention of Source Documents

The Investigator must maintain source documents such as laboratory reports, ECGs, consultation reports, and complete history and physical examination reports.

23 February 2021 CONFIDENTIAL Page 56 of 60

Protocol Number: TEN-02-402

Edition No. 2

#### 13.2 Retention of Essential Documents

Essential documents should be maintained for at least 11 years based upon the Sponsor's requirements and may be required to be maintained longer based upon applicable regional regulatory requirements. The Investigator/institution should take measures to prevent accidental or premature destruction of these documents. Should the Investigator/institution not be able to maintain the records for this period of time, the Investigator/institution must inform the Sponsor in writing, via certified mail, at least 90 days prior to the destruction of any study documents, so that the Sponsor has the option, at the Sponsor's expense, to have the records stored for a longer period of time. It is the Sponsor's responsibility to inform the Investigator or institution as to when these documents no longer need to be retained.

